5.2 Voriconazole Dosage and Administration

Voriconazole is an FDA approved triazole antifungal agent. The primary mode of action of voriconazole is the inhibition of fungal ergosterol biosynthesis by inhibiting the cytochrome P450 mediated 14 alpha-lanosterol demethylation. Voriconazole has demonstrated *in vitro* activity against *Aspergillus* and *Fusarium* species and is an approved treatment for serious fungal infections. Intrastromal Voriconazole injection is practice for the treatment of moderate to severe filamentous fungal corneal ulcers at Aravind Eye Hospital, Pondicherry.

Voriconazole is available as 1 mg of white lyophilised powder in a glass vial (VOZOLE PF; Aurolab, India). The powder is reconstituted with 2 mL of lactated Ringer's solution to a concentration of 0.5 mg/mL (50 mg/0.1 mL). A dose of 50 mg/0.1 mL reconstituted intrastromal voriconazole is prepared just prior to administration.

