4.4.2 Intrastromal Voriconazole Injection

The intrastromal injection will be performed in the operating theatre under the operating microscope by the cornea surgeon under peribulbar anesthesia and with full aseptic precautions. This will be performed within 24 hours of the baseline visit. Voriconazole 0.5 mg/ml solution will be loaded in a 1 ml tuberculin syringe with a 30-gauge needle. With the bevel down, the needle will be inserted obliquely starting in the adjacent uninvolved stroma to reach the infiltrate at the mid-stromal level (as the intended level for drug deposition) in each case. The drug is then injected and the amount of hydration of the cornea is used as a guide to assess the area saturated with medication. Once the desired amount of hydration is achieved, the plunger is withdrawn slightly to ensure discontinuation of the capillary column and thus prevent back-leakage of the drug. Four to six divided doses are given around the infiltrate/s to surround the entire circumference of the lesion.

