5. STUDY MEDICATIONS

The following medications will be administered for treatment purposes: Natamycin 5%, Moxifloxacin 0.5%, Homatropine 2%, and Voriconazole 0.5mg/ml injection.

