5.1 Treatment schedule for study medications

In the first 3 days all patients will receive hourly 5% Natamycin drops, 0.5% Moxifloxacin drops for prophylaxis every two hours while awake, and 2% homatropine drops TID. The aforementioned drugs will be used for FDA approved indications. Study participants will then be randomized to intrastromal injection with voriconazole plus natamycin versus natamycin. All medications will be protected and only appropriate personnel will administer the drugs.

Table 2: Dosing schedule for Medications

Medication	Day 1-3	Day 1 Procedure	Day 3 Procedure	After Day 3 Scraping	Day 5 Procedure
Natamycin 5%	Every hour			Physician determined	
Moxifloxacin 0.5%	6 times/day			Physician determined	
Homatropine 2%	3 times/day			Physician determined	
Voriconazole 0.5 mg/ml		50mg/0.1ml administered via intrastromal injection	50mg/0.1ml administered via intrastromal injection	Physician determined	50mg/0.1ml administered via intrastromal injection

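### Protocol Section 5.2 and Table 2 express the intrastromal voriconazole in two ways that differ 1000-fold and must be reconciled.

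*Protocol*

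**What the plan says.** The protocol gives the strength or amount of the injected voriconazole in four places.

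- **Section 5.2** starts from the product: "Voriconazole is available as 1 mg of white lyophilised powder in a glass vial". It continues: "The powder is reconstituted with 2 mL of lactated" Ringer's, which yields a "solution to a concentration of 0.5 mg/mL (50 mg/0.1 mL", the bracket being offered as the equivalent of the first figure. The next sentence uses the bracketed figure as the dose: "A dose of 50 mg/0.1 mL reconstituted intrastromal voriconazole is prepared just prior to administration".
- **Section 5.1, Table 2** labels the row "Voriconazole 0.5 mg/ml" and enters "50mg/0.1ml administered via intrastromal injection" under each of the Day 1, Day 3 and Day 5 procedures.
- **Section 5** lists the drug as "Voriconazole 0.5mg/ml injection", with no amount per injection.
- **Section 4.4.2** states: "Voriconazole 0.5 mg/ml solution will be loaded in a 1 ml tuberculin syringe with a 30-gauge needle". It gives no milligram amount and no fixed volume. The surgeon is guided by corneal hydration and injects four to six portions around the lesion.

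The 0.5 mg/mL figure therefore appears four times (4.4.2, 5, the Table 2 row label, 5.2). The 50 mg/0.1 mL figure appears five times (three cells of Table 2, twice in 5.2). The SAP gives no dose.

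**The concern.** Section 5.2 and Table 2 each contain both figures, and the two cannot describe the same solution. The conflict is in the dosage section and the dosing table for the experimental drug, which only the voriconazole arm receives, at three procedures (Sections 3.4.2 and 4.4.3). The 50 mg/0.1 mL entries are also the protocol's only numerical statement of an amount per injection, so a reader cannot turn to another section to settle it.

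Two things are at stake. The first is safety: anyone preparing or checking an injection from Table 2 meets two strengths a thousandfold apart. The second is the definition of the treatment under test: as written, the amount given cannot be verified against the protocol, and the intervention cannot be described without ambiguity when the trial is reported.

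**Working it through.** Inputs, all from the protocol:

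- vial content 1 mg (Section 5.2)
- diluent volume 2 mL (Section 5.2)
- stated strength 0.5 mg/mL (Sections 4.4.2, 5, 5.1 row label, 5.2)
- stated amount 50 mg per 0.1 mL (Section 5.1 cells, Section 5.2)

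**Step 1. Reproduce the first figure in Section 5.2.** Concentration = vial content / diluent volume = 1 mg / 2 mL = 0.5 mg/mL. This follows from the stated vial and diluent.

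**Step 2. Amount in 0.1 mL at that concentration.** 0.5 mg/mL × 0.1 mL = 0.05 mg, which is 50 micrograms. The bracketed figure of 50 mg is not reproduced: 50 / 0.05 = 1000.

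**Step 3. Convert the second figure to a strength.** 50 mg / 0.1 mL = 500 mg/mL, and 500 / 0.5 = 1000. The factor is the same by either route.

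**Step 4. Check against the described product.** At 1 mg per vial, 50 mg is the content of 50 / 1 = 50 vials. At 0.5 mg/mL it would occupy 50 / 0.5 = 100 mL. Neither is possible in 0.1 mL drawn from one vial made up to 2 mL, so the preparation described could not deliver 50 mg.

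| Expression | mg per 0.1 mL | mg/mL |
|---|---|---|
| 0.5 mg/mL | 0.05 | 0.5 |
| 50 mg/0.1 mL | 50 | 500 |
| Ratio | 1000 | 1000 |

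**Reach of the Table 2 entries.** SAP Section 2 plans 70 participants and Protocol Section 1.3 specifies 1:1 allocation, so 70 / 2 = 35 in the voriconazole arm. With three procedures each, 35 × 3 = 105 planned procedures. This assumes that the target is met, the split is even, every procedure is done, and the sample-size re-evaluation in SAP Section 6 leaves the target at 70. The count shows only how often the entry would apply. It does not measure the discrepancy.

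**The case against.** The strongest objection is that the conflict may not be in the source document. It turns on one character in a unit. A factor of exactly 1000, identical in all five places, is what a systematically misread micro sign would produce, and a PDF-reading fault is not a fault in the plan. No micro sign or Greek letter occurs anywhere in the available text.

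This is plausible but not shown. Other special characters came through, including the greater-than-or-equal sign in the ulcer classification table (Section 4.2) and an arrow in Section 4.5.2, so symbols were not lost wholesale. The mg form also appears in two typographic styles, with a space in Section 5.2 and without one in Table 2, although a consistent typing slip or a font-specific reading error could explain both. The text alone cannot decide, so a check of the source has to come first.

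A second objection is that the error is harmless, because a 1 mg vial cannot supply 50 mg and Section 4.4.2 has the surgeon work from hydration, not from a set amount. Both facts are correct. They rule out reading this as evidence of overdosing, and they mean that Table 2 may not be the only instruction determining what is injected. They do not make a dosing table acceptable when it cannot be followed as written.

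A third objection is that Sections 4.4.2 and 5 are not internally inconsistent. That stands: the conflict itself lies in Sections 5.1 and 5.2. The other two are included only because all four must agree after any correction.

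**Conclusion.** The concern holds on the protocol text as supplied. Section 5.2 and Table 2 each equate or pair 0.5 mg/mL with 50 mg/0.1 mL, and these differ by exactly 1000: 0.05 mg against 50 mg per 0.1 mL, or 0.5 mg/mL against 500 mg/mL. The arithmetic needs no assumption beyond the stated vial content, diluent volume and units, and no other section removes the conflict.

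Confidence is high that the available text contradicts itself and medium that the source document does, because of the possible lost micro sign. If the source reads mg, this must be fixed: it is a contradictory dose statement for the experimental injection in the sections that specify dosing. If the source shows a micro sign in all five places, the point falls away.

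**What to change.** 1. Check the source PDF at the five places where 50 mg/0.1 mL appears: the three procedure cells of Table 2 and the two mentions in Section 5.2.
2. If the source reads mg in any of them, the sponsor and pharmacy should confirm the intended figures and correct the protocol so that vial content, diluent volume, concentration and amount per stated volume agree arithmetically in Sections 4.4.2, 5, 5.1 and 5.2. This review does not say which figure is right.

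The cost is a source check and, if needed, a short protocol correction. The design, sample size and analysis do not change.

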5.3 Possible Side Effects of Study Medications

Natamycin: eye irritation, swelling, pain and/or redness, discharge

Voriconazole: eye irritation, swelling, pain and/or redness, discharge

Moxifloxacin: eye irritation, swelling, pain, or redness

Homatropine: eye irritation, swelling, pain, or redness; Eye dilation may result in temporary blurred vision, light sensitivity, and increased heart rate.

6. PROTECTION OF HUMAN SUBJECTS

6.1 Institutional Review Board Approval

6.1.1 Aravind Eye Hospital, Ethics Review Committee

The Ethics Committee will review the study protocol annually for ethical approval.

6.1.2 University of California, San Francisco Committee on Human Research (CHR)

The UCSF CHR will review the study protocol annually for ethical approval.

6.2 Informed Consent

Aravind personnel will obtain full written consent from each patient. The primary surgeon will screen participants and determine their eligibility. He/she will clearly explain the process and risks involved and will also ask the patient to sign any necessary consent documents. The study participant will have 7 visits total per eye included in the study over 3 months; visits include hospitalization for the first 7. The patient has the ability to withdraw at any time and will not be forced into anything with which he/she is not comfortable. Consent documents have been uploaded to the IRB application.

6.3 Risks to Study Participants

Fungal keratitis is a very serious sight threatening infection. The best therapy is still not known; therefore many treatments including topical and oral antifungals are often administered. Intrastromal Voriconazole injection, in addition to oral and topical antifungals, is current practice for the treatment of moderate to severe filamentous fungal corneal ulcers at Aravind Eye Hospital, Pondicherry. Participants in the study have the same risks as those undergoing treatment of their fungal keratitis who choose not to participate in the study.

It is not known whether or not the addition of oral antifungal is of benefit to these patients. The Mycotic Ulcer Treatment Trial II is an ongoing large prospective randomized controlled two arm clinical trial looking at whether or not oral voriconazole is of benefit in addition to topical antifungals. In this study we are asking patients to delay oral therapy for 3 days.

As with any surgery, there are risks associated with intrastromal injection which include risk of infection, or damage to the cornea, which could result in vision loss. There is a very small risk of full thickness perforation with the needle. If this were to occur, it would most likely be self-sealing, but may increase the risk of endophthalmitis, a severe sight threatening intraocular infection. Sterile precautions will be taken to ensure decreased risk of infection.

There may be some discomfort during follow-up testing (BSCVA, IOP, slit lamp, Pachymeter, Topography, and OCT testing and photo imaging of the eye), but this will be kept to a minimum. The participant will be asked to tell the doctor if any of this testing feels painful. There may be a medication reaction such as eye irritation, swelling, pain, redness, or discharge. If this occurs the risks of stopping the medication must be weighed against the severity of infection and other treatment options.

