Mycotic Antimicrobial Localized Injection (MALIN) is a randomized, masked, two-arm clinical trial. The purpose of the study is to determine differences in microbiological cure for 3-day repeat cultures between different antifungal treatments. There will be 1:1 randomization to one of these two treatment groups: 1) Topical natamycin plus intrastromal voriconazole injection or 2) Topical natamycin alone. The enrollment period will be 3 months.

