3.4 Study visits

3.4.1 Baseline Visit. During this visit, eligible patients at Pondicherry will be enrolled in the study and will give consent. The baseline patient form will be completed and BSCVA obtained. All study participants will begin topical therapy with hourly 5% natamycin immediately. They will have baseline photography and OCT. They will then be randomized to either intrastromal voriconazole plus natamycin or topical natamycin alone. Those randomized to intrastromal injection will undergo this procedure in the operating theatre within 24 hours. They will have an additional 2 stromal injections: one on the 3rd day and one on the 5th day. All patients will be admitted to the inpatient setting until the 7th day.

3.4.2 Procedure visit. Within 24 hours of the baseline visit study participants randomized to intrastromal voriconazole will undergo injection in the operating theatre. They will have 2 additional rounds of intrastromal voriconazole injections: one on the 3rd day and one on the 5th day of the study.

3.4.3 Day 3 visit. During this visit, study participants will have slit lamp examination and undergo repeat scraping and culture of the corneal ulcer. Adverse events will also be assessed and recorded. Thereafter, all additional treatments including but not limited to topical voriconazole, or oral ketoconazole, will be at the clinician's discretion. The treating physician will remain masked to treatment arm. After the scraping and culture have been performed, participants randomized to receive intrastromal voriconazole injections will receive an additional injection of voriconazole in the operating theatre.

3.4.5 Day 5 visit. On day 5 participants randomized to receive intrastromal voriconazole injections will receive their final injection of voriconazole in the operating theatre.

3.4.6 Week 1 visit. Approximately one week from enrollment patients will undergo repeat scraping and culture. No other study visit information will be gathered during this visit, therefore any further examination, testing, or treatment will be at the discretion of the treating physician. After the Day 7th day, patients may be discharged from the inpatient setting.

3.4.7 One Month visit. During this visit, study participants will have their BSCVA, slit lamp examination, and OCT performed during this visit. Photography will also be performed. Adverse events will be reviewed and recorded.

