4.3 Medical management protocol

In the first 3 days all patients will receive hourly 5% Natamycin, 0.5% Moxifloxacin for prophylaxis every two hours while awake, and 2% homatropine TID. They will be randomized to intrastromal injection with voriconazole versus sham injection. This study requires 7 visits over 3 months including baseline visit, procedure visit, 3-day follow-up and procedure visit, 5-day procedure visit, 1-week follow-up, 1-month and 3-month follow-up. After the 3-day repeat culture visit additional treatments may be added per clinician preference including but not limited to topical voriconazole and oral Ketoconazole.

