4.4 Procedures

4.4.1 Corneal Gram Stain and Culture

After patient history and slit lamp examination at the enrollment visit (Day 0), corneal scraping is performed to determine the eligibility of the patient (positive fungal stain and negative bacterial stain). Corneal scraping is recommended as standard of care for all corneal ulcer patients at the Aravind Eye Hospitals. There is a small risk to patients of inducing a perforation, worsening an epithelial defect, or contaminating an ulcer, and patients are duly informed of these risks prior to the taking of the corneal scrape.

Corneal scraping will be obtained as follows:

- A drop of topical anesthetic (0.5% tetracaine or 4% lidocaine) is administered to the eye to be examined.
- Aseptic technique is used to obtain each corneal scrape. A flame-sterilized Kimura spatula is used, with the aid of slit lamp magnification, to obtain a scrape from the leading edge and base of the corneal ulcer. The Kimura spatula is again flame sterilized between the takings of each sample.
- Two scrapings are smeared directly on to two separate glass microbiology slides for Gram stain and for KOH wet mount (if necessary, Giemsa or Gram Stain can be used to identify fungal elements as well).
- Three further scrapings are taken and directly inoculated on to sheep's blood agar, chocolate agar, potato dextrose agar or Sabouraud's agar for bacterial and fungal culture.

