4.4.3 Additional Injections

An additional two rounds of intrastromal injections will be performed at 3 days and 5 days post enrollment in the voriconazole injection arm only. This MUST be performed after the 3-day repeat culture visit. The study coordinator and treating physician will be aware of the treatment assignment; however, the follow-up physician and microbiologist will remain masked to treatment arm.

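### Section 6.3 equates participants' risks with those of non-participants, although the protocol delays oral therapy, assigns controls no injection at least until the Day 3 culture, and requires two repeat scrapings that 6.3 does not list

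*Protocol*

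**What the plan says.** Protocol 6.3 makes three statements close together:

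- On the site's usual care: "Intrastromal Voriconazole injection, in addition to oral and topical antifungals, is current practice for the treatment of moderate to severe filamentous fungal corneal ulcers".
- On the risk of taking part: "Participants in the study have the same risks as those undergoing treatment of their fungal keratitis who choose not to participate in the study".
- On oral antifungals: "In this study we are asking patients to delay oral therapy for 3 days".

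The arms are given in 1.3 as "1) Topical natamycin plus intrastromal voriconazole injection or 2) Topical natamycin alone". Section 4.4.3 says the two further rounds of injection "will be performed at 3 days and 5 days post enrollment in the voriconazole injection arm only". Section 4.3 describes the comparison differently: "They will be randomized to intrastromal injection with voriconazole versus sham injection".

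Section 3.4.3 requires a repeat scrape and culture at Day 3. Section 3.4.6 requires another: "Approximately one week from enrollment patients will undergo repeat scraping and culture". On the hazards of scraping, 4.4.1 says: "There is a small risk to patients of inducing a perforation, worsening an epithelial defect, or contaminating an ulcer". It adds that patients are told of these risks before the scrape is taken.

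Section 3.4.6 also says that nothing else is collected as study information at the Week 1 visit. Section 3.6 says subjects are asked about adverse events at each study visit, and the schedule in 3.5 marks a Follow-up form at both Day 3 and Week 1.

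**The concern.** The equal-risk sentence compares participants with patients at the same hospital who are treated outside the study. It is true only if study care adds nothing to that treatment, removes nothing from it and postpones nothing. The protocol does all three.

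Both ethics committees review this document (6.1.1, 6.1.2), and the surgeon must explain the risks when seeking consent (6.2). If the risk section says that taking part makes no difference, a committee or patient relying on it would not learn that the repeat scrapings for the primary outcome and the 7-day culture outcome carry hazards the protocol itself names.

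There is a related gap in data capture. Perforation is a secondary outcome. The Week 1 visit includes a procedure with a stated perforation risk, yet 3.4.6 can be read as excluding adverse-event questions at that visit. After Week 1 the patient may go home, and the next visit description that mentions adverse events is Month 1.

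**Working it through.** The plan gives no figure to reproduce. The check sets the passages side by side and then counts.

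**Step 1. What a non-participant receives.** By 6.3, current practice at the site is intrastromal voriconazole plus oral and topical antifungals. Section 5.2 also describes the injection as practice at the hospital.

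**Step 2. What a participant receives, compared with that.**

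| Element | Site practice, per the protocol | In the study | Same? |
|---|---|---|---|
| Oral antifungals | Part of current practice (6.3) | Delayed 3 days, both arms (6.3) | No |
| Intrastromal voriconazole | Part of current practice (6.3) | Voriconazole arm: yes. Controls: not assigned (1.3, 3.3, 3.4.1); further rounds in the voriconazole arm only (4.4.3) | Not for controls, at least until the Day 3 culture |
| Day 0 scrape | Recommended standard of care (4.4.1) | Done for eligibility (4.4.1) | Yes |
| Day 3 and Week 1 scrapes | Not stated | Required of everyone (3.4.3, 3.4.6, 3.5) | Cannot be shown to be the same |
| Sham injection | Not mentioned | Named in 4.3; natamycin alone in 1.3, 3.3, 3.4.1 and 5.1 | Unresolved conflict |

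The first two rows are enough to contradict an unqualified claim of equal risk. The Day 3 limit in the second row is there because 3.4.3 and 4.3 leave added treatment after the Day 3 culture to the clinician, with an open-ended list. Later injection of a control eye is therefore not expressly barred.

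**Step 3. What 6.3 lists.** It covers infection, corneal damage with vision loss, needle perforation and endophthalmitis from the injection. It also covers discomfort from follow-up tests (acuity, pressure, slit lamp, pachymetry, topography, OCT, photography) and medication reactions. Scraping appears nowhere in the section.

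**Step 4. Counts.** Inputs: 70 participants (SAP section 2), 1:1 allocation (Protocol 1.3), and smear/culture at baseline, Day 3 and Week 1 (Protocol 3.5).

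- Participants with the oral-therapy delay: all 70.
- Controls: 70 ÷ 2 = 35.
- Repeat scrapings per participant: 3 scheduled − 1 at baseline = 2.
- Repeat scrapings in total: 2 × 70 = 140. This is a maximum, since it assumes everyone reaches Week 1 and is scraped there.

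The documents describe the scraping risk only as small and give no rate, so no expected number of complications is calculated. The contradiction does not depend on one.

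**Step 5. Recording.** Day 3: 3.4.3 provides for adverse-event assessment, and a Follow-up form is scheduled. Week 1: a Follow-up form is scheduled (3.5) and 3.6 requires questioning at each visit, but 3.4.6 says nothing beyond the scrape and culture is collected. These Week 1 passages do not agree.

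**The case against.** The strongest reply is that this is one badly worded sentence in a section that is otherwise open about risk. Much of that reply stands.

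- **Disclosure.** A reader might infer that the protocol hides the oral delay or treats study risks as nil. It does neither. Section 6.3 states the delay in the next paragraph, says the benefit of oral antifungals is unknown, and lists the injection risks. Section 4.4.1 says patients are told of scraping risks beforehand. The fault is the equal-risk sentence and the absence of scraping from 6.3.
- **Direction of risk.** A reader might infer that participants, or controls in particular, are worse off. The documents do not support that. The Introduction describes mixed evidence on intrastromal voriconazole, including a randomized trial with better 3-month acuity in its topical group, and controls avoid the needle risks. The risks differ; the net balance is what the trial is asking.
- **Repeat scraping.** A reader might infer that 4.4.1 limits standard of care to the diagnostic scrape. Its sentence refers to all corneal ulcer patients but sits with the Day 0 eligibility scrape. Whether repeat scraping is routine outside the study is not stated.
- **Consent form.** It was not available for this review and may already be correct.
- **Forms.** The lack of a Procedure form at Week 1 means nothing, since that form follows the injections exactly. Adverse-event reporting (3.6), a medical monitor and a DSMC (SAP section 6) exist.
- **Compensation.** A reader might tie the point to 6.6. That section offers no compensation for research-related injury, so calling an event study-related would change no entitlement under it.

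None of this makes the equal-risk sentence true, and the Week 1 conflict between 3.4.6 and 3.6 remains.

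**Conclusion.** The point holds as a contradiction in the text. As written, the statement in 6.3 is inconsistent with the 3-day oral delay for all 70 planned participants and with the assignment of about 35 controls to no intrastromal injection at least until the Day 3 culture. It also leaves out up to 140 protocol-required repeat scrapings whose hazards are named in 4.4.1.

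This rests on taking the description of current practice in 6.3 at face value and on the planned sample size. No complication rate is assumed. The sham wording in 4.3 is an unresolved inconsistency: if a sham is given, it is a further difference for controls; if not, 4.3 does not describe the trial.

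The matter does not touch the primary analysis or the power. It should be corrected because it concerns what ethics committees are told about risk, and because the Week 1 passages leave it unclear whether complications of a risk-bearing procedure are asked about at that visit.

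**What to change.** 1. In 6.3, delete or qualify the equal-risk sentence.
2. In its place, state by arm how study care differs from the site's current practice: the oral-therapy delay (both arms), assignment to injection or to no injection, and the repeat scrapings at Day 3 and Week 1 with the risks named in 4.4.1. If repeat scraping is routine at the site, say so.
3. Reconcile the sham injection in 4.3 with natamycin alone in 1.3, 3.3, 3.4.1 and 5.1, and make the risk text match whichever applies.
4. Check that the consent form agrees with the corrected section.
5. Reconcile 3.4.6 with 3.6 by recording the three scraping complications named in 4.4.1 on the Follow-up forms already scheduled for Day 3 and Week 1. Record occurrence only. Do not ask for attribution to injection: under 4.1 the physician doing the repeat scraping is masked, and such an item would invite guessing or unmasking.

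The cost is an ethics amendment, a few items on existing forms and a slightly less favourable risk statement. No change of treatment is proposed.
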